comparisons, one-way analysis of variance (ANOVA) followed by Dunnett's test, where appropriate, was used to determine the statistical significance of the difference between means. The follow-up parametric data were compared using the paired student's t-test. Non-parametric data were determined by chi-squared tests. Analyses of primary and secondary outcomes are performed with the use of time-to-event methods according to the intention-to-treat principle. All analyses were two-sided, and $p<0.05$ was considered statistically significant. Statistical analyses were performed using Prism version 5 (GraphPad Software Inc., La Jolla, CA, USA).

5. Handling of Missing Data :

Omit the cases with missing data and analyze the remaining data.

2. Introduction and Rationale

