2.5 Regulatory

This study will be conducted in compliance with the protocol approved by the Institutional Review Board, and according to Good Clinical Practice standards. No deviation from the protocol will be implemented without the prior review and approval of the IRB except where

it may be necessary to eliminate an immediate hazard to a research subject. In such case, the deviation will be reported to the IRB as soon as possible.

3. Objectives and Endpoints

3.1 Study Objectives:

3.1.1 Primary objective:

To evaluate the benefit of high protein supplementation and core muscle rehabilitation and trunk NMES intervention in weaning from ventilator

3.1.2 Secondary objectives:

The impact of renal function and digestion status after high protein intake
The benefit in nutrition status and diaphragm weakness and the correlation to weaning status

3.1.3 Other exploratory objectives (if any):

1.2 Study endpoints:

3.2.1 Primary endpoint:

Weaning rate

(weaning success defined as weaning from ventilator for 5 consecutive days)

3.2.2 Secondary endpoints:

In hospital mortality, Length of mechanical ventilator usage,
Length of ICU stay and total length of hospitalization,
Serum albumin level improvement, Creatinine clearance rate

3.2.3 Other exploratory endpoints (if any):

4. Study Design

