The age, gender, smoking history, diagnosis, length of mechanical ventilator use, APACHE II will be recorded. The pulmonary performance, including tidal volume, maximal inspiratory pressure (MIP), cough function, peak inspiratory pressure (PIP), positive end-expiratory pressure (PEEP), lung compliance, airway resistance, blood gas analysis, Barthel index, serum albumin, creatinine, electrolytes will record before, during (twice per week) and after intervention. We also follow the outcome of hospitalization, including the weaning rate, mortality, length of mechanical ventilator use, length of ICU stay and total length of hospitalization. We will further evaluate the diaphragm movement. Ultrasound was performed at the end of exhalation (without stimulation) to measure the thickness of the diaphragm, twice per week of participation, and then weekly until RCC discharge. All measurements were taken from muscles on the right-hand side of the participant by the same assessor at all assessment sessions. For the diaphragm, the probe was placed parallel to the anterior axillary line in the intercostal space between the 9th and 10th rib and moved in the cranial and caudal directions until the pleural line was identified. From this point, the probe was moved approximately 1 or 2 intercostal spaces lower to identify the costal diaphragm in the zone of apposition. In all measurements, the probe was placed perpendicular to the skin. We will analyze the diaphragm movement, thickness and the correlation with successful weaning rate.

Flow Chart :

Abbreviation: RCC, respiratory care center; PMV, prolonged mechanical ventilation; NM, neuromuscular; DVT, deep vein thrombosis; CHF, congestive heart failure; BMI, body mass index; TV, tidal volume; MIP, maximal inspiratory pressure; PIP, peak inspiratory pressure; PEEP, positive end-expiratory pressure; UC, usual care; HP, high protein, NMES, neuromuscular electrical stimulation

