11.2.1 Efficacy analysis

Kaplan–Meier survival analysis was performed to assess weaning and survival outcomes.

Mann Whitney test was used for compare non-parametric data (weaning rate, length of ventilator use, length of ICU stay and length of hospitalization).

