11.3 Analysis Population

All subjects randomized.

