11.4 Procedure for accounting for missing, unused and spurious data

The incomplete clinical data and sequencing data with poor quality will be excluded in the study.

12. Direct access to source data/documents

Investigators permit IRB to access to the source data of experiment for trial-related monitoring, audits and regulatory inspection.

13. Ethical considerations

This study will be conducted according to Taiwan and international standards of Good Clinical Practice for all studies. Applicable government regulations and Chang Gung Medical Foundation research policies and procedures will also be followed.

This protocol and any amendments will be submitted to the Chang Gung Medical Foundation Institutional Review Board (IRB) for formal approval to conduct the study. The decision of the IRB concerning the conduct of the study will be made in writing to the investigator.

All subjects for this study will be provided a consent form describing this study and providing sufficient information for subjects to make an informed decision about their participation in this study. This consent form will be submitted with the protocol for review and approval by the IRB. The formal consent of a subject, using the IRB-approved consent form, will be obtained before that subject is submitted to any study procedure. This consent form must be signed by the subject or legally acceptable surrogate, and the investigator-designated research professional obtaining the consent.

14. Data handling and keeping

Clinical samples will be collected in Chang Gung Medical Foundation. The sequencing data will be stored in computers of laboratory with an electronic encryption. The clinical and source data can only be assessed by clinical doctors and investigators of the study.

15. Financing and Insurance

Apply for CMRP support. The funders had no role in the study design, data collection and analysis, decision to publish, or manuscript preparation.

16. References

Background

Ventilator-induced diaphragm dysfunction (VIDD)

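### No rule covers a patient who leaves hospital alive and still ventilated, and the plan's texts point to truncation, omission or censoring, each of which can hide a weaning benefit in the duration outcomes

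*Combined protocol and SAP*

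**What the plan says.** The primary endpoint in section 3.2.1 is a weaning rate, with "weaning success defined as weaning from ventilator for 5 consecutive days". No time window is given. Length of ventilator use and length of hospitalization are named as secondary endpoints in 3.2.2, without start dates, stop dates or scoring rules. Sections 4.1 and 7 follow these as outcomes of the hospitalization. The last scheduled visit in 4.3 is day 28±1, and no follow-up after discharge is described.

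On analysis, the texts differ:

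- Section 11.2.1: "Mann Whitney test was used for compare non-parametric data (weaning rate, length of ventilator use, length of ICU stay and length of hospitalization".
- The same section: "Kaplan–Meier survival analysis was performed to assess weaning and survival outcomes". Censoring is not defined.
- Synopsis, Statistical Methods: "Analyses of primary and secondary outcomes are performed with the use of time-to-event methods according to the intention-to-treat principle".
- Section 11.3, analysis population: "All subjects randomized".
- Synopsis, Handling of Missing Data: "Omit the cases with missing data and analyze the remaining data".
- Section 11.4: "The incomplete clinical data and sequencing data with poor quality will be excluded in the study".

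None of these says what value, rank or censoring applies to a patient who leaves alive and still on the ventilator.

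**The concern.** A trial with a weaning rate as its endpoint expects some patients not to wean. Some of those who survive may leave hospital while still ventilated. Their ventilation has no observed end within the follow-up described, yet section 11.2.1 needs one length from each patient in order to rank them.

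Each treatment that the documents allow has its own fault:

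- **Stopping at leaving** (11.2.1 read with 11.3) ranks a weaning failure as short ventilation when departure is early relative to weaning times.
- **Omission** (the synopsis rule and 11.4) removes the failures, who carry the treatment difference.
- **Censoring at leaving** (time-to-event methods, Kaplan–Meier) treats these patients as still as likely to wean as those who remain.

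Hospital stay has a different problem. Its end date is observed, so the missing-data rules do not apply, and an early ventilated departure is scored like an early recovery.

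At stake is whether the duration outcomes can show a weaning benefit that is really there. This is separate from the handling of deaths: ranking deaths worst does nothing for survivors who never weaned.

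**Working it through.** **The plan's own figure.** Section 11.1 gives 10 usual-care patients and 30 in each of three other groups: 10 + 3 × 30 = 100, which reproduces the stated total. The plan gives no power, effect size, weaning rate or rate of ventilated discharge, so every rate below is an assumption.

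**Assumed inputs.** 35% v 70% weaned, with weaning days uniform on 3 to 26 in both arms. 10% die in each arm and are ranked worst. The rest are alive and never weaned: 100 − 35 − 10 = 55% v 100 − 70 − 10 = 20%. All of them leave ventilated, on days uniform within a stated window. The test is a two-sided Mann-Whitney at 0.05, simulated with 1,500 runs per setting.

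**Ventilator length, 30 v 30.** Repeated runs differ by a few hundredths.

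| Leaving window (days) | Stopped at leaving | Omitted | Never-weaned ranked worst |
|---|---|---|---|
| 7–28 | 0.06–0.08 | 0.05–0.08 | 0.6–0.7 |
| 14–28 | 0.19–0.20 | 0.05–0.08 | 0.6–0.7 |
| 21–28 | 0.41–0.44 | 0.05–0.08 | 0.6–0.7 |
| 21–42 | 0.50–0.54 | 0.05–0.08 | 0.6–0.7 |

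In the last column, about 0.7 applies when never-weaned survivors tie with deaths, and about 0.6 when they rank just better than deaths.

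**Why omission loses the effect.** Expected counts per 30 patients are 10.5 weaned, 3 dead and 16.5 leaving ventilated, against 21, 3 and 6. After omission, 13.5 and 24 remain. The weaned patients have the same timing in both arms. The only difference left is the share of deaths, 3/13.5 = 22% v 3/24 = 12.5%.

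**Censoring, limiting cases.** Take deaths as at risk without an event. If all ventilated departures come after the last weaning, Kaplan–Meier gives 35% v 70%, a difference of 35 points. If all come before the first weaning, it gives 10.5/13.5 = 77.8% v 21/24 = 87.5%, a difference of 9.7 points. Departures in between distort the curves to an intermediate degree. This reading was not simulated.

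**Other sample sizes and effects.** With a 10-patient control arm, power is about 0.05–0.28 if stopped, 0.04–0.06 if omitted and 0.3–0.4 if ranked worst. With 50% v 60% weaned at 30 v 30, stopping gives 0.06–0.10 and worst rank 0.10–0.12.

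**A second set of assumptions.** Here 60% v 30% leave ventilated, there are no deaths, weaning days are uniform on 5 to 28, and departure is within ±4 days of day 10, 14, 21 or 28. The probability that a control patient has the longer ventilation is 0.41, 0.47, 0.56 and 0.64 if stopped at leaving, about 0.50 if omitted, and about 0.65 if ranked worst.

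**Hospital stay.** No simulation is needed to see the direction. A patient who leaves ventilated on day 18 has a stay of 18 days and ranks better than one who is weaned and discharged on day 22.

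**The case against.** A reader might infer that the plan, as written, ranks these failures as short ventilation. The documents do not support that. No text stops ventilator use at discharge, and a patient without a value cannot be ranked. The missing-data rules point to omission, and the synopsis points to time-to-event methods. Even under truncation the rank is short only if departure is early; with departure around days 21 to 42 these patients fall in the longer part of the distribution. This objection stands, and it limits the point to a missing rule with conflicting substitutes.

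A reader might also infer that the result could reverse. On the main assumptions, a significant result in the wrong direction occurred in under 1% of runs. It reached 22% only under the second set, with departure around day 10. Reversal is therefore not a general expectation.

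The phrase "twice per week of participation, and then weekly until RCC discharge" in section 4.1 might be read as defining when lengths are measured. It is only the diaphragm ultrasound schedule.

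It is also fair to say that the trial calls itself exploratory, that 35% v 70% is a large assumed effect, that the comparison with usual care has only 10 controls, and that the documents never say how often ventilated discharge occurs. These limit the size that can be claimed. They do not rescue the plan, because where the weaning effect is large, omission loses nearly all of it and truncation loses a part that depends on when patients happen to leave.

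**Conclusion.** The concern holds as a gap with consequences. The plan does not say how to handle discharge alive on the ventilator, and its own texts lead to three different analyses of ventilator length. On the assumed 35% v 70% weaning with 30 v 30, power is about 0.06 to 0.5 or 0.05 to 0.08 under the two simulated readings, against 0.6 to 0.7 with a defined worst rank. With a modest effect the loss is small. For hospital stay the fault follows directly from the text and needs no assumed rate, although its size does.

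The primary weaning proportion is not affected, provided that these patients are counted as not weaned under the 5-day definition. The harm falls on the secondary lengths and on the Kaplan–Meier weaning analysis. All magnitudes rest on assumed weaning, death and departure rates, and on every surviving non-weaner leaving ventilated, which is the most unfavourable case. This should be changed, with medium confidence in its practical size.

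**What to change.** In section 11.2.1:

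1. Set a fixed horizon from randomisation, for example the existing day 28 visit, and define the start and stop of ventilator use. State whether the 5 days must be completed by then.
2. Give every surviving patient who has not met the 5-day definition by that horizon, including those who left ventilated, a prespecified unfavourable rank for ventilator length. Ventilator-free days of 0 is one way; a worst rank placed next to deaths is another.
3. In the time-to-weaning analysis, keep these patients at risk without an event to the horizon instead of censoring them on leaving.
4. Analyse hospital stay as time to discharge alive and off the ventilator, at least alongside raw length of stay.
5. Reconcile the synopsis (time-to-event methods, missing data) with 11.2.1, 11.3 and 11.4, so that these patients are not dropped as missing or incomplete.

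The cost is SAP wording and one data field: on or off the ventilator at discharge. The downside is that patients who wean elsewhere before the horizon count as failures unless their status is obtained.

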11.2.2 Safety analysis

Wilcoxon matched-pairs signed rank test was used to compare parametric data (difference of baseline and follow-up serum creatinine and creatinine clearance)

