11.2 Planned Statistical methods of analysis

Categorical variables were expressed as count and percentage. Parametric data were expressed as mean \pm standard deviation (SD). A Student's t-test was used to compare parametric data. Fisher's exact test was used to compare non-parametric data. We used a receiver operating characteristic (ROC) curve to identify the optimal cut-off-value for the maximum multiplication of sensitivity and specificity. Logistic regression was used for multivariate analysis. Kaplan–Meier survival analysis was performed to assess weaning and survival outcomes. Statistical significance was set at a p-value < 0.05 . Statistical analyses were performed using GraphPad Prism version 8 (GraphPad Software, La Jolla, CA, USA) and IBM SPSS Statistics 26 (SPSS, Chicago, IL, USA).

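### Renal safety is tested only before versus after, without the randomised usual-care arm, and no suitable between-arm method is assigned to creatinine clearance or albumin

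*Combined protocol and SAP*

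**What the plan says.** Section 11.2.2 is a single sentence: "Wilcoxon matched-pairs signed rank test was used to compare parametric data (difference of baseline and follow-up serum creatinine and creatinine clearance". Section 11.2.3 adds no further analysis.

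The secondary objectives (section 3.1.2) include "The impact of renal function and digestion status after high protein intake", and the secondary endpoints (section 3.2.2) include "Serum albumin level improvement, Creatinine clearance rate".

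Other statistical text that might apply:

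- Section 11.2.1 assigns the Mann-Whitney test to "non-parametric data (weaning rate, length of ventilator use, length of ICU stay and length of hospitalization", and Kaplan-Meier to weaning and survival. Creatinine clearance and albumin are not listed.
- The synopsis (Statistical methods) compares group means by "one-way analysis of variance (ANOVA) followed by" Dunnett's test, where appropriate. It names no endpoint.
- The synopsis also says: "Analyses of primary and secondary outcomes are performed with the use of time-to-event methods according to the intention-to-treat principle".
- For follow-up data the synopsis says: "The follow-up parametric data were compared using the paired" Student's t-test.
- Section 11.2 says that a Student's "t-test was used to compare parametric data", without stating paired or two-sample, arms or endpoint.

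**The concern.** Whether high protein intake changes renal function is a question about a treatment effect. It also carries weight for safety, because the protocol does not lower protein provision if renal failure occurs. Randomisation supplies a usual-care arm to answer it, but the one method tied by name to creatinine and creatinine clearance does not use that arm.

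Patients ventilated for more than 21 days may recover, deteriorate or regress to the mean over the treatment weeks whatever they are fed. A before-after test counts all of that as change. It can signal an effect where protein has none. It can also miss harm, if usual-care patients improve and high-protein patients stay level.

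Two details are open as well. The text does not say whether the test is run per arm or on everyone pooled. It does not say which of the repeated follow-up values is used; section 2.4 has creatinine followed at least twice a week and section 8 weekly, and these need to be reconciled. For albumin, the analyst could choose among a paired test, ANOVA, a t-test or a time-to-event method after seeing the data.

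**Working it through.** **Inputs from the documents.** Usual care 10 patients, three other arms of 30 (section 11.1); two-sided testing (synopsis) at 0.05 (section 11.2.4); 20% loss (section 4.2). The arm sizes reproduce the stated total: 10 + 3×30 = 100. A 20% loss leaves 100×0.8 = 80, or 24 per large arm and 8 in usual care. (Section 4.2 labels 100 as evaluable and 80 as enrolled, whereas section 11.1 enrols 100.)

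**Assumptions.** The documents give no SD, expected trend or renal margin. Effects are therefore in SD units of the change from baseline, with normal changes and independent arms.

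**1. False signal.** Suppose there is no treatment effect and every arm shares a trend of d SD. Let a and b be the power of a paired t-test (noncentral t) at n=30 and n=10.

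- At least one of three large arms significant, usual care not: (1−(1−a)³)(1−b)
- One given large arm significant, usual care not: a(1−b)
- Pooled: power of the paired test at n=100

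| d | a | b | Any of three | One given arm | Pooled |
|---|---|---|---|---|---|
| 0 | 0.050 | 0.050 | 0.135 | 0.048 | 0.050 |
| 0.1 | 0.083 | 0.059 | 0.215 | 0.078 | 0.168 |
| 0.2 | 0.185 | 0.088 | 0.419 | 0.169 | 0.508 |
| 0.3 | 0.355 | 0.136 | 0.633 | 0.307 | 0.844 |
| 0.4 | 0.563 | 0.205 | 0.728 | 0.447 | 0.977 |
| 0.7 | 0.959 | 0.506 | 0.494 | 0.474 | not run |
| 1.0 | 1.000 | 0.803 | 0.197 | 0.197 | not run |

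Example at d=0.2: (1−0.815³)×0.912 ≈ 0.42.

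With 24 and 8 patients the any-arm figures are 0.367, 0.708 and 0.319 at d = 0.2, 0.4 and 1.0. The pooled test at n=80 gives 0.143, 0.424, 0.755 and 0.942 at d = 0.1 to 0.4. Simulating the signed-rank test itself (5,000 runs, 30 and 10) gives any-arm figures of 0.13, 0.40, 0.63, 0.73, 0.51 and 0.22 at d = 0, 0.2, 0.3, 0.4, 0.7 and 1.0, so the t approximation is adequate.

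**2. A between-arm test under the same shared trend** (4,000 runs, 30 versus 10). At d = 0, 0.25, 0.5 and 0.75 the within-arm Wilcoxon test rejects in 5%, 25%, 73% and 97% of trials. The two-sample t-test on change stays at about 5% throughout.

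**3. Masked harm.** Usual care improves and one high-protein arm does not change.

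| Improvement in usual care | Within-arm test significant | Between-arm t-test significant |
|---|---|---|
| 0.5 SD | 4.6% | 27% |
| 1.0 SD | 4.5% | 77% |

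**4. Precision of the between-arm comparison.** The 95% half-width on unadjusted change is t(0.975, n1+n2−2)×√(1/n1+1/n2).

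| Comparison | Half-width (SD) |
|---|---|
| 30 vs 10 | 0.739 |
| 90 vs 10 | 0.661 |
| 24 vs 8 | 0.834 |
| 72 vs 8 | 0.742 |

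Dunnett's critical value by simulation (three arms of 30, control of 10, 96 df) is 2.31, so the adjusted half-width is 2.31×√(1/30+1/10) = 0.84 SD. Power for a true 0.5 SD difference is about 27% (30 vs 10) or 32% (90 vs 10). Adjusting for baseline multiplies the half-width by √(1−r²)/√(2(1−r)): 0.866, 0.922 and 0.975 at baseline to follow-up correlations r = 0.5, 0.7 and 0.9.

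**The case against.** The strongest reply is that the plan already contains a comparison with control. Dunnett's test compares several arms with one control, and section 11.2.1 assigns other methods to weaning, survival and the durations. By elimination, albumin and creatinine clearance are what remains for it. That reading is possible, and it would be wrong to say the documents contain no between-group method for means. But the sentence is qualified, names no endpoint and sits beside a time-to-event rule for all secondary outcomes. For creatinine and creatinine clearance the specific rule in 11.2.2 points elsewhere.

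A second reply is that no text says a significant high-protein arm beside a non-significant usual-care arm will be read as an effect of protein. That stands: this way of reading the results is an assumption of the arm-by-arm figures, as is the shared trend. The 13.5% at no trend also comes from having three arms and counts changes in either direction; for one given arm it is about 5%. The pooled and masked-harm results do not need that pattern, and the defect does not depend on any one percentage.

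Thirdly, the study is described as exploratory, the renal objective is secondary, and ten controls give little precision. All true. That excuses low power, not leaving the randomised control out of a stated objective. A wide interval against usual care shows the uncertainty that a paired p-value hides.

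**Conclusion.** The concern holds. The only rule written for renal safety is a before-after test that cannot answer the renal objective. Creatinine clearance and albumin have no fitting between-arm method assigned to them: the generic ones are unassigned, and time-to-event methods do not suit a continuous laboratory value.

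That conclusion rests on the text alone. The size of the error depends on an unknown trend. Under the stated assumptions, a shared trend of a few tenths of an SD is enough to make misleading significance common, whether the test is read per arm or pooled. The plan should be changed on this point. The change gives a valid estimate but not a precise one.

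**What to change.** Replace section 11.2.2 with wording along these lines:

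> Serum creatinine, creatinine clearance and serum albumin are compared between arms in all randomised patients by ANCOVA adjusted for the baseline value at one named follow-up day. Each high-protein arm minus usual care is reported with a 95% CI, using Dunnett's adjustment. For the renal variables, all high-protein arms combined minus usual care is also reported with a 95% CI. Paired within-arm changes are descriptive. Absence of renal harm is not concluded from p>0.05, nor without a margin stated before the data are analysed.

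A mixed model over the scheduled visits is an acceptable alternative. Choose one, and settle any log transformation for skewed renal values, before the data are seen. State how patients who die or withdraw before the named day are handled, since ANCOVA at one day cannot use a patient without a value. The investigators set any margin.

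Limit the synopsis time-to-event sentence to outcomes that are times to an event, and reconcile its paired t-test with the Wilcoxon test. State that with 10 controls only large renal effects can be ruled out.

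The cost is SAP wording and a small analysis in SPSS, which section 11.2 already lists. No new data are needed. The drawback is the wide intervals shown above, which baseline adjustment narrows only modestly.

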9.1 Definitions and reports of Adverse Events

All adverse events that occur after the informed consent is signed (including run-in) must be recorded on the adverse event CRF (paper and/or electronic) whether or not related to study

agent. AE Data Elements including:

- AE reported date
- AE Verbatim Term
- CTCAE Term (v 5.1)
- Event onset date and event ended date
- Severity grade
- Attribution to study agent (relatedness)
- Whether or not the event was reported as a Serious Adverse Event (SAE)
- Action taken with the study agent
- Outcome of the event
- Comments

Identify the adverse event using the NCI Common Terminology Criteria for Adverse Events (CTCAE) version 5.0. The CTCAE provides descriptive terminology and a grading scale for each adverse event listed.

AEs will be assessed according to the CTCAE grade associated with the AE term. AEs that do not have a corresponding CTCAE term will be assessed according to their impact on the participant's ability to perform daily activities as follows:

Grade	Severity	Description
1	Mild	
• Barely noticeable, does not influence functioning• Causing no limitations of usual activities
2	Moderate	
• Makes participant uncomfortable, influences functioning• Causing some limitations of usual activities
3	Severe	
• Severe discomfort, treatment needed• Severe and undesirable, causing inability to carry out usual activities
4	Life threatening	
• Immediate risk of death• Life threatening or disabling
5	Fatal	
• Causes death of the participant

The possibility that the adverse event is related to study drug will be classified as one of the

following: not related, unlikely, possible, probable, definite.

DEFINITION of Serious Adverse Events: ICH Guideline E2A and GCP of Taiwan define serious adverse events as those events, occurring at any dose, which meet any of the following criteria:

- Results in death
- Is life threatening (Note: the term life-threatening refers to an event in which the patient was at risk of death at the time of the event; it does not refer to an event which hypothetically might have caused death if it were more severe).
- Requires inpatient hospitalization or prolongation of existing hospitalization
- Results in persistent or significant disability/incapacity
- Is a congenital abnormality/birth defect

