11.1 Sample size Determination

This is an exploratory research, we determine the enrolled number according to the

number of patients admitted to RCC annually.

Ten patients will be assigned to UC group.

Thirty patients will be included in another 3 group.

A total 100 patients will be enrolled.

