11.2.3 Additional analysis

Not applicable

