11.2.4 The level of significance

A p-value less than 0.05 was considered significant and was denoted by * and p-value less than 0.01 was denoted by **.

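### The only planned safety analysis is a paired rank test of creatinine and creatinine clearance: it can miss serious renal injury in a minority, and no count of affected patients by arm is planned

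*Combined protocol and SAP*

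**What the plan says.** Under safety analysis, section 11.2.2 of the combined protocol and SAP has one entry: "Wilcoxon matched-pairs signed rank test was used to compare parametric data (difference of baseline and follow-up serum creatinine and creatinine clearance"). It does not say which follow-up reading is used, whether the test is run by arm, or what change counts as injury. Section 11.2.3, on additional analyses, reads "Not applicable". Section 11.2.4 sets the criterion, "A p-value less than 0.05 was considered significant", and the statistical methods in the synopsis add "All analyses were two-sided".

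Other places bear on renal function:

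- Section 3.1.2 makes the renal effect of high protein intake a secondary objective, and section 3.2.2 lists creatinine clearance as a secondary endpoint.
- Section 4.1 names creatinine in a list of measurements that ends "electrolytes will record before, during (twice per week) and after intervention". Section 2.4 also has creatinine followed two or more times a week, whereas section 8 has it followed weekly.
- Section 9.1 states "AEs will be assessed according to the CTCAE grade associated with the AE term". Section 9.2 counts as adverse events those laboratory abnormalities that the investigator judges clinically important.
- The synopsis omits cases with missing data, and section 11.4 excludes incomplete clinical data. Section 5.3 makes a return to ICU a ground for withdrawal.

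**The concern.** The question for a safety analysis is how many patients in each arm had serious renal injury. A paired rank test answers another question: whether the typical patient's value moved. It has three weaknesses here.

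1. **Scale.** Each patient contributes only a sign and a rank. A doubling and a fivefold rise count the same if both exceed every other change. A few such patients can be outweighed by many small falls.
2. **No comparator.** A within-patient test cannot attribute a change to the diet, nor show that usual care would have produced the same change.
3. **Who is in the pairs.** With complete cases only and an undefined follow-up value, a patient who leaves for the ICU or dies before that reading may have no pair, and a rise that has resolved by then is not seen by the test.

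At stake is the trial's answer on one of its own secondary objectives. A non-significant result, or a significant fall, could be reported although a meaningful share of an arm had renal injury.

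**Working it through.** **Arm sizes.** Section 11.1 says "Ten patients will be assigned to UC group" and "Thirty patients will be included in another 3 group". Reading thirty as the size of each of three arms gives 10 + 3 × 30 = 100, the stated total. Reading it as the sum over three arms gives 10 + 30 = 40, which does not match. With the 20% dropout in section 4.2, an arm of 30 leaves 30 × 0.8 = 24. (Section 4.2 labels 100 as evaluable and 80 as enrolled; 80 / (1 − 0.20) = 100 suggests that the labels are swapped.) The plan gives no SD, injury rate or power for the renal analysis, so the creatinine values below are assumptions.

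**Constructed arm of 30.** Let baseline be 1.0 mg/dL, 27 patients fall by 0.02 to 0.20, and 3 at least double.

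- All ranks: 30 × 31 / 2 = 465.
- The falls take ranks 1 to 27: 27 × 28 / 2 = 378.
- The doublings take ranks 28 + 29 + 30 = 87.
- Expected sum on each side under no shift: 465 / 2 = 232.5.
- Two-sided p = 0.002, in the direction of a fall. The median change is −0.10 and the mean change is +0.002.

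Because the mean is also near zero, the paired t-test that the synopsis names for follow-up data would not show the injury either.

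| Patients in pairs | Doublings | Rank sum, falls v rises | p | Direction |
|---|---|---|---|---|
| 30 | 3 (10%) | 378 v 87 | 0.002 | fall |
| 30 | 4 (13%) | 351 v 114 | 0.014 | fall |
| 30 | 5 (17%) | 325 v 140 | 0.058 | not significant |
| 24 | 3 (12.5%) | 231 v 69 | 0.019 | fall |

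**Simulation.** Assumed model: baseline lognormal (median 0.9, log SD 0.5); log change Normal(drift, 0.20), plus log 2 in a random fraction of patients; signed-rank test at two-sided 0.05. Share of trials of n = 30 with a significant rise:

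| Fraction doubling | No drift | 5% downward | 10% downward |
|---|---|---|---|
| 10% | 18% | 2% | under 1% |
| 15% | 29% | 6% | 1% |
| 20% | 44% | 15% | 3% |

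In the 15% row with a 10% downward drift, about 7% of trials show a significant fall.

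If all 90 diet patients were pooled, with no drift, a rise is detected in about 45% to 47% of trials at 10% doubling and about 89% at 20%. With 10% doubling and a 10% downward drift, the pooled test shows a fall in about 39% and a rise in none.

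A second set of assumptions (log-change SD 0.15, baseline log SD 0.4, n = 30) gives the same pattern. With 10% doubling, a rise is found in 17%, 0.7% and 0% of trials as drift goes from none to 5% to 10% downward, and in the last case 33% show a fall.

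**What counts by arm would give.** Exact 95% intervals: 3/30 = 10% (2.1% to 26.5%); 0/10 = 0% (0% to 30.8%, upper limit 1 − 0.025^(1/10)). Fisher's exact test of 10 controls against 30 has power 3.7% for 5% v 20% and 25% for 5% v 30%.

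**Side effect of taking the worst of several readings.** Assume no injury, log SD 0.20 and six independent readings (twice a week for three weeks), so 30 × 6 = 180 readings per arm. One reading exceeds 1.5 times baseline with probability 0.0213, and 1 − (1 − 0.0213)^180 = 98% of arms show at least one. For 2 times baseline the probability is 0.00026, and about 5% of arms show at least one.

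**The case against.** The strongest reply is that the safety data do not rest on this test alone. Under sections 9.1 and 9.2, a creatinine rise that the investigator judges clinically important is an adverse event, recorded whether or not related, and graded by CTCAE. That covers rises that resolve or precede withdrawal. This stands, and a reader who inferred that such injury goes unrecorded, or that CTCAE is never applied to creatinine, would be wrong. What it does not supply is an analysis: entry depends on individual judgement and no adverse event table by arm is planned.

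Other stronger readings also fail:

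- **That renal function has no other possible analysis.** Creatinine clearance is a secondary endpoint, and the synopsis gives generic methods that could reach it (ANOVA with Dunnett's test, paired t-test, time-to-event). Section 11.2 also offers Fisher's exact test. None names a renal event.
- **That the plan chose to discard all but one follow-up reading.** Section 11.2.2 does not define follow-up, and section 4.3 schedules creatinine clearance at several visits. The fault shown is that the reading is undefined.
- **That section 2.4 calls renal harm a known risk.** It reports no significant renal effect in a preliminary study and plans monitoring.
- **That the test will usually mislead.** With no drift, and pooled, it often detects a rise. The 39% figure needs both pooling and a downward drift, and the documents state neither.

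It is also fair that counts against 10 controls have little power, and that the trial is exploratory. Both argue for intervals in place of a test, not against counting.

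**Conclusion.** The concern holds in limited form. The one analysis listed under safety can miss serious renal injury in a minority. It can be significant for a fall while 10% to 13% of an arm of 30 double their creatinine. That result is arithmetic on ranks and needs no power assumption, only that most of the other patients fall slightly.

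How often this would happen is uncertain. At 15% doubling in 30 patients, detection runs from about 29% with no drift to 1% with a 10% downward drift. The SD, injury rate and drift are all assumed. The gap that is certain is that no count of patients with renal injury, by arm and against usual care, is planned, although the readings and a grading scale are already in the protocol. Nothing here judges the protein target or its handling in renal failure.

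**What to change.** In section 11.2.2:

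1. Make the main renal safety summary, by arm, the number and percentage of patients by worst post-baseline CTCAE v5.0 creatinine grade, shown beside the baseline grade. Use all scheduled readings, including those before withdrawal or death, so that no patient with a post-baseline reading is dropped as incomplete.
2. Give exact 95% intervals for each arm and for the difference from usual care.
3. Keep the paired test, if wanted, as a descriptive supplement by arm, with the follow-up reading defined. State that non-significance is not evidence of no renal harm.
4. Reconcile the creatinine sampling frequency: sections 2.4 and 4.1 have it twice a week or more, section 8 weekly. Reconcile the CTCAE version too, since section 9.1 gives both 5.1 and 5.0.

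The cost is SAP wording and one table from values already collected. Two downsides should be stated. Taking the worst of several readings inflates low-grade counts in every arm, so emphasis belongs on the higher grades and the contrast between arms. Intervals against 10 controls will be wide: even 0/10 is compatible with a true rate of up to 30.8%. Grading also discards some information, which the retained continuous summary offsets.
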